## **Research Application Completion Instructions**

### For Research Application Review:

- Review and update the cover page
- Review sections 1-2
- Complete Sections 3-15
- Please fully read Sections 16-18

The Research Application is intended to provide study protocol for assessment of feasibility and alignment with OptumLabs' mission by OptumLabs Research team staff members. It is understood that the study protocol is a living document and research designs (such as planned study variables or statistical analyses) may change as projects progress. OptumLabs recommends that Research Applications be annotated with changes throughout the life of the project so that an accurate account of data set construction, variable operationalization, and statistical analysis is maintained. Research Applications are reviewed by the OptumLabs Research Review Committee (RRC). More information on this review can be found on The Bridge.

We recognize that certain Partners may have existing formats for detailed study protocols. Partners may submit material requested in Section 3 in their own format as a supplement to the application, provided that: 1) all of the content requested in the application is included; and 2) all other application sections are completed and submitted along with the supplement.

### 1. Project Summary

### a. Problem Formulation / Hypothesis

While prospectively planned clinical trial data remains the cornerstone of regulatory submissions, to date real world evidence (RWE) has not been routinely utilized or accepted for drug approval due to a number of challenges. Recent interest in RWE studies has been driven by the desire to bring innovative products to patients more quickly than the traditional drug development path involving RCTs. This desire has been expressed through regulatory mandates. The Observational Patient Evidence for Regulatory Approval and uNderstanding Disease (OPERAND) program is designed to better inform the use of RWE from retrospective observational studies in medicine and regulatory decision-making. We propose a program that will first use retrospective observational data to determine if such data can confirm previously published RCT results and, if successful, extend the use of the data for other potential applications.

### b. Disease Area and Project Type Categorization

OptumLabs tracks information about projects conducted by our Partners for the purpose of examining trends in research. Please help us with these efforts by answering the two questions below:

Please select one "project type" or theme that best describes your project. We recognize that categories are not mutually exclusive, and your project may fall into several categories.

Methods and Innovation in Observational Data Analysis

Please select the disease area which best represents the focus of your project. If multiple disease areas are included in your project, please select the disease area that is most prevalent or you feel is of most interest. Chapters of the ICD10 coding system are provided to aid your selection.

Not Applicable

### c. Study Purpose and Objectives

The purpose of this study to replicate two previously published randomized controlled trials of pharmacological products that were used as the basis of marketing approval by the FDA, the

ROCKET Atrial Fibrillation study and the LEAD-2 study. For each trial, the initial objective is to mimic the inclusion/exclusion criteria, endpoint definitions, exposure windows, and other design features of each study as closely as possible. Then, using a series of multivariate methods, average treatment effect (ATE) estimates will be produced and compared to those reported in the original publication.

The specific objectives for this project are:

- 1. Mimic the inclusion/exclusion criteria of the trial, as well as the primary endpoint, and follow-up period. Carefully document your definitions as one of the goals of OPERAND is to understand how differences in researcher decision-making may introduce variability into ATE estimates.
- 2. Create three patient cohorts for each study: (1) using the full sample of patients with claims data, irrespective of whether they have linked EHR data, (2) the sample of claims that link with EHR data, and (3) the sample of patients with claims plus EHR data. (See discussion below on comparisons of these samples.)
- 3. Perform multivariate analyses to estimate ATEs using the following:
  - A single equation method such as generalized linear models (GLM) to introduce the treatment variable as a covariate. Please describe your criteria/method for selecting the other covariates included in the model.
  - Propensity score matching. We leave the specification of variables to be included in the propensity score model, as well as other decisions, such as the size of the calipers, to the research team but please describe these decisions and criteria fully.
  - Inverse probability weights. Same documentation requirements as the other two methods.
  - At least one other appropriate method at the discretion of the researcher (e.g., regression discontinuity methods, instrumental variables, differences in differences, G-estimation, targeted maximum likelihood estimation (TLME)). More than one method is encouraged.
- 4. Estimate separate sets of models for the three samples of patients. Linking to EHR will substantially reduce the sample but provide additional covariate controls. Use bootstrapping methods for all ATE estimates from the observational data to evaluate the effects of alternative methods and data samples on estimation bias (relative to the published RCT ATE) and standard errors.
- 5. How do the ATE estimates from the 3 samples compare?
- 6. Compare the results from the multivariate analyses to the published estimates of ATE using two methods:
  - Regulatory agreement—defined as statistically significant result with directional equivalence between the RCT and observational study.
  - Estimate agreement—defined as the point estimate of the observational study falling within the 95% confidence interval of the ATE from the RCT

using the reported standard errors of the RCT to define the confidence interval.

7. Are the results similar? If not, why do you think they differ? Do you have greater confidence in some of the observational results than others? Why or why not?

### d. Data Sources

We will use the following currently available data from 1994-2018. Note that for the final primary analyses we will probably restrict the range to years during which all compared interventions (for each trial emulation) were approved for the indication evaluated in the emulated trial. That is to say, for the LEAD-2 trial emulation, we will use data from 2010 onwards and for the ROCKET trial emulation we will use data from 2011 onwards. For the final emulation analyses and the "extended population" analyses (if requested) we will update the year range as 2019 data become available in OptumLabs.

- Administrative claims data: Enrollment files
- Administrative claims data: Medical claims transactions
- Administrative claims data: Pharmacy claims transactions
- $\boxtimes$  PanTher (EHR-derived)
- ⊠ Laboratory results claims-sourced/health plan affiliated
- Supplemental Oncology Data
- ⊠ Race/ethnicity
- Mortality Status
- ⊠ Cost data: insurer-paid amounts
- ⊠ Cost data: patient-paid amounts
- Benefits Design
- □ Patient distance traveled
- Socioeconomic Status Data
- ⊠ Health Risk Assessment (HRA)
- ⊠ Consumer/Lifestyle data
- $\boxtimes$  RUCA codes
- $\Box$  Area Health Resource Files (AHRF)
- □ American Hospital Association (AHA) Data
- $\boxtimes$  Expanded discharge status field

Based on the above and the information in the Research Application Appendix, this study will utilize the following view (select one):

NATIONAL
UNIFIED
LIFESTYLE
SES

```
STATE
MORTALITY
COUNTY
ZIP5
```

Study subjects will include:

- $\boxtimes$  Commercial enrollees
- ⊠ Medicare Advantage enrollees

### 2. Research Plan

### a. Population, study cohorts, and special subgroups of interest

**Trial emulations:** Table 1 summarizes our plan for the emulation of the ROCKET trial and Table 2 summarizes our plan for the LEAD-2 trial. We now provide some additional information on cross-cutting issues that apply to both emulations.

Cohort construction: We will follow the recommendation in the RFP regarding the strategy for cohort construction. Specifically, we will start with the claims data first and then match the claims cohort to the subset of patients who also have EHR data. We will compare the results of three cohort creation and data selection strategies: (1) patients with claims irrespective of EHR status; (2) patients with claims who also have EHR data available but using only data from the claims subset; (3) patients with both claims and EHR data. We do note that we followed this strategy for our PCORI-funded Methods Research Award that used OptumLabs data to perform a number of trial emulations (see **Section 7** for additional information).

Eligibility criteria: To determine eligibility for our emulations, we will rely heavily on diagnostic and procedure codes from claims or EHR data to operationalize the trial inclusion and exclusion criteria. Whenever possible, we will implement validated algorithms that have been used in prior studies of similar data (we discuss this further in **Section 3b**). We will attempt to emulate the study design of the emulated trials to the extent possible. For example, in the ROCKET trial emulation we will implement a new-user (incident user) designs and in the LEAD-2 trial we will emulate the run-in design using the methods described previously by [name] and Robins.

Continuous enrollement (pre-baseline): To implement the trial eligibility criteria and be able to extract baseline covariate values for statistical analyses, we will require that patients remained continuously enrolled in their plan for at least 6 months before baseline. Note that only a subset of a patient's medical encounters are captured in EHR data, even if the patient remains continuously enrolled in the same insurance plan, because patients may choose to receive care by providers who do not contribute data to OptumLabs.

Covariate assessment period (pre-baseline): In all emulations, we will collect covariate information over the 6 months before the start of treatment. When multiple laboratory measurements are available in that period (e.g., in emulations using both claims and EHR data), we will use the values most proximal to baseline.

Enrollment and followup periods: We anticipate limiting the period during which individuals in the data can be eligible for our emulations to the periods when all the compared interventions were available. We will emulate the baseline time (time zero) choice and followup duration of the

emulated trials (see **Tables 1** and **2** for details). We will not require a minimum follow-up duration to avoid introducing selection bias. We will follow individuals until the end of followup in the corresponding emulated trial, the occurrence of an outcome event, death, or loss to follow-up, whichever occurred first. Loss to follow-up will be defined as plan dis-enrollment from the claims data.

Expanded population analyses (pending TEP approval): If the conduct of the expanded population analyses is requested by the TEP, we will use the same specifications as for the emulations described above (and in **Tables 1** and **2**), except for the eligibility criteria, which will be systematically relaxed. Our understanding, based on the RFP, is that the TEP will provide input for how to systematically "expand the aperture". For qualitative restrictions, the criteria can be broadened by simply removing one or more restrictions (e.g., by allowing individuals at low risk of stroke in the rivaroxaban analyses, even though such individuals will have been excluded from the ROCKET trial emulation). For quantitative selection criteria (e.g., age), the criteria can be broadened gradually (e.g., require age <80 years, <85 years, <90 years in the LEAD-2 emulation). Natural as these choices for relaxing the eligibility criteria may appear, they create a multivariate "criteria relaxation surface" that cannot be exhaustively explored (once the number of criteria being relaxed grows above a small number, the size of the space of possible observational studies becomes very large). We will reduce the dimensionality of the space by proposing "bundles" of criteria that define 3-5 new target patient populations, that is to say, we will combine versions of the criteria in such a way as to induce a spectrum ranging from a "highly selected" population (often, but not necessarily, this will coincide with the actual trial emulation) to a "minimally selected/unselected" population. These bundles of criteria will be provided to the TEP for review along with the other deliverables on September 2019.

We intend to use the same analysis plan for the expanded population analyses as for the emulation analyses. Please see **Section 11** for details of our analysis plan.

 Table 1: Main aspects of the ROCKET trial emulation.

Component of	ROCKET trial emulation (criteria abstracted from the trial protocol)	Notes for the operationalization of the eligibility criteria in OptumLabs (see
emulation		also our remarks regarding variable definitions in Section 3b)
Eligibility criteria	– Age ≥18 years	
 
Age criteria will be implemented using the corresponding claims or EHR field.
 

	- Non-valvular atrial fibrillation, as documented on electrocardiography. Atrial	- Non-valvular atrial fibrillation will be defined using inpatient or outpatient claims,
	fibrillation must be documented by ECG evidence (e.g., 12-lead ECG,	not electrocardiography. All other valvular conditions described in the ROCKET
	rhythm strip, Holter, pacemaker interrogation) within 30 days before	trial's protocol (available as Appendix to the NEJM article reporting the trial results)
	randomization. In addition, subjects must have medical evidence of atrial	will be reflected in the routinely collected data using established code algorithms.
	fibrillation within 1 year before and at least one day before the qualifying	
 
As per the RFP, we will not use left ventricular ejection fraction as an eligibility
 

	ECG evidence. This could be obtained from the subject's medical record.	criterion in our main analysis. We may opt to use it in a stability analysis (see
	– Moderate-to-high risk for stroke. Elevated risk was indicated by a history of	paragraph on "Stability analyses"), but we will base our judgement on the
	stroke, transient ischemic attack, or systemic embolism or at least two of the	completeness of the available data in the EHR.
	following risk factors: heart failure or a left ventricular ejection fraction of 35%	– We will obtain a claims-based version of the CHADS2 score using methods
	or less, hypertension, age $\geq$ /5 years, or the presence of diabetes mellitus	analogous to those described previously."
	(i.e., a CHADS2 score of 2 or more, on a scale ranging from 1 to 6, with	- Conditions such as hypertension, diabetes, recent stroke or transient ischemic
	higher scores indicating a greater risk of stroke).	attack, indications for anticoagulation other than atrial fibrillation (e.g., recent venous
	- The proportion of patients who had not had a previous ischemic stroke,	thromboembolism), anemia, significant liver disease, etc., will be coded using
	two risk factors was limited to 10% of the select factors had no more than	established diagnostic algorithms (e.g., as for our phor work using OptumLabs data),
	remainder of patients were required to have had either provinue	The aritarian about contars having up to 10% of patients who had not had a
	thromboombolism or throo or more risk factors	- The chilehon about centers having up to 10% of patients who had not had a
	– Exclusion Criteria: hemodynamically significant mitral valve stenosis:	had no more than two risk factors can be enforced by random sampling after the
	prosthetic heart valve (annuloplasty with or without prosthetic ring	cohort is formed (repeat sampling with appropriate adjustment of the sampling
	commissurotomy and/or valvuloplasty are permitted); planned cardioversion	variance estimator can be used to ensure that no information is discarded).
	(electrical or pharmacological): transient atrial fibrillation caused by a	- Pregnant women will be excluded.
	reversible disorder (e.g., thyrotoxicosis, PE, recent surgery, MI); known	- Criteria related to planned treatments (e.g., "planned cardioversion") will not be
	presence of atrial myxoma or left ventricular thrombus: active endocarditis:	reflected in the routinely collected data (because intent cannot be determined
	active internal bleeding; history of or condition associated with increased	retrospectively); instead, we will take the initiation of the treatments of interest to
	bleeding risk including; planned invasive procedure with potential for	imply that the criterion was not met. Similar certain exclusion criteria will also not
	uncontrolled bleeding, including major surgery; platelet count <90,000/µL at	need to be reflected because the initiation of treatment is indicative of them not
	the screening visit; sustained uncontrolled hypertension: systolic blood	being present (e.g., in clinical practice anticoagulation therapy is not started in the
	pressure ≥180 mmHg or diastolic blood pressure ≥100 mmHg; severe,	presence of active internal bleeding).
	disabling stroke within 3 months or any stroke within 14 days before the	- Platelet count criteria will not be used in the claims analyses because of expected
	randomization visit; transient ischemic attack within 3 days before the	high degree of missingness. We might use them in EMR-based analyses.
	randomization visit; indication for anticoagulant therapy for a condition other	- Aspirin-related criteria will not be implemented because claims (and EHR) data is
	than atrial fibrillation (e.g., VTE); treatment with aspirin, intravenous	highly incomplete for over-the-counter medications. Again, we will take treatment
	antiplatelets within 5 days before randomization, fibrinolytics within 10 days	initiation as implying that co-treatments were appropriately chosen.
	before randomization; anti-inflammatory drug; systemic treatment with a	
 
Other medication exclusions will be implemented using pharmacy claims.
 

	strong inhibitor of cytochrome P450 3A4 within 4 days before randomization,	- Creatinine clearance will also not be used as an eligibility criterion in the main
	or planned treatment during the time period of the study; treatment with a	analyses. In our prior work the missingness in serum creatinine values was fairly
	strong inducer of cytochrome P450 3A4, within 4 days before randomization,	high (more than 30% even among subsets with diagnostic or procedure codes
	or planned treatment during the time period of the study; anemia; anemia	related to chronic kidney disease).
	(nemoglobin <10 g/dL) at the screening visit; pregnancy or breast-feeding;	- The exclusion criterion related to serious illness with limited life expectancy will be
	any other contraindication to warrarin; known HIV intection at time of	operationalized by excluding individuals with severe liness at baseline (e.g.,
	screening, calculated GLGR <30 mL/min at the screening visit, known	auvanceu stage chronic kioney disease, metastatic non-meianoma skin cancer, etc.)
	significant liver disease; senous concomitant limess associated with a life	
	expectancy of less than 2 years.	

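### ROCKET emulation: the fixed 6-month covariate window is not reconciled with the open-ended history of stroke, TIA or systemic embolism in Table 1

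*Protocol*

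**What the plan says.** Protocol Section 2.a, on the covariate assessment period, fixes one window for both emulations: "we will collect covariate information over the 6 months before the start of treatment". The preceding paragraph sets the enrollment rule: "we will require that patients remained continuously enrolled in their plan for at least 6 months before baseline". Its stated purpose covers eligibility as well as covariates: "To implement the trial eligibility criteria and be able to extract baseline covariate values for statistical analyses".

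Table 1 gives the trial's stroke-risk criterion without a time limit: "Elevated risk was indicated by a history of" stroke, TIA or systemic embolism, or else at least two listed risk factors. Patients without such an event and with no more than two risk factors are capped at 10%, and the notes column proposes to enforce the cap by random sampling.

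On operationalization, the notes column says "We will obtain a claims-based version of the CHADS2 score using methods" analogous to those of a cited study, and gives no look-back. It also has an entry beginning "Conditions such as hypertension, diabetes, recent stroke or transient ischemic" attack, to be coded with established algorithms. The word recent there fits the trial's short stroke and TIA exclusions (3 months, 14 days, 3 days). It does not define how far back a history of stroke is sought.

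Section 2.b defers the choice of codes and code positions to the start of the project. It does not list the length of the look-back among the deferred items.

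**The concern.** Prior stroke, TIA or systemic embolism does three jobs in this emulation: it qualifies patients, it decides who falls under the 10% cap, and it is an obvious candidate confounder of anticoagulant choice and later stroke. A 6-month window sees only part of an unlimited history. An unseen event is stored as a plain no, not as a missing value, so neither the complete-case analysis nor the multiple imputation in Section 9.a would touch it.

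Every Table 3 estimator relies on measured covariates. Double robustness protects against a misspecified working model, not against a mismeasured confounder. The emulation is judged by whether its estimate agrees with the trial's, so a look-back artifact could be read as evidence about real-world data in general. Section 1.c also says that one aim of the program is to learn how researchers' choices move the estimates. Look-back length is such a choice, and no stability analysis of it is planned.

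**Working it through.** The plan gives no figure for this point, so the check has two parts: tracing the rules, and an illustration on assumed values.

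**1. Tracing the rules.** Take a patient whose only stroke was 8 months before treatment and was not recoded in the last 6 months.

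- *If eligibility uses all available claims:* the patient qualifies through the stroke, yet enters the propensity and outcome models with no stroke history.
- *If eligibility uses the same 6 months:* the result depends on the other risk factors in Table 1. With none or one, the patient appears ineligible and is dropped. With exactly two, the patient moves into the group capped at 10% and may be sampled out. With three or more, the patient stays in but is still miscoded in the models.

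Adjustment is affected on either reading. The cohort is affected only on the second, and the text does not say which applies.

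**2. How many could be miscoded.** Let p be the true prevalence of history, s the share that the window captures, and assume no false positives. The share wrongly recorded as having no history is p(1 − s). With p from 0.2 to 0.6 and s from 0.5 to 0.9 (all assumed), this runs from 0.2 × 0.1 = 2% to 0.6 × 0.5 = 30%.

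**3. Residual confounding.** Inputs:

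- Treated share w = 19,710 / (19,710 + 48,380) = 0.289, from the preliminary counts in Section 9.b. These count people with at least one claim, not eligible initiators.
- Assumed: p₁ = 0.30 (rivaroxaban), p₀ = 0.40 (warfarin), history doubles outcome risk, specificity 1, true treatment ratio 1.

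Formulas:

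- Unadjusted ratio = (1 + p₁)/(1 + p₀) = 1.30/1.40 = 0.929.
- True history among those recorded as negative: q = p(1 − s)/(1 − ps).
- Pooled recorded prevalence: P = s[w·p₁ + (1 − w)·p₀].
- Adjusted ratio = [2P + (1 − P)(1 + q₁)] / [2P + (1 − P)(1 + q₀)].

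At s = 0.5: q₁ = 0.15/0.85 = 0.176; q₀ = 0.20/0.80 = 0.250; P = 0.5 × (0.289 × 0.30 + 0.711 × 0.40) = 0.186. The adjusted ratio is 1.329/1.389 = 0.957. On the log scale, ln 0.957 / ln 0.929 leaves 59% of the confounding.

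| Share captured, s | Adjusted ratio | Log-scale confounding left |
|---|---|---|
| 0.5 | 0.957 | 59% |
| 0.6 | 0.964 | 49% |
| 0.8 | 0.980 | 27% |

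The residual bias is therefore about 2% to 4% on the ratio scale.

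**4. Sensitivity to the assumptions.** With p₁ = 0.15, p₀ = 0.20 or 0.25, an outcome ratio of 2 or 3, s from 0.5 to 0.9 and equal group sizes, the unadjusted ratio runs from 0.867 to 0.958 and the adjusted ratio from 0.924 to 0.995. That is a residual bias of about 0.5% to 8%. The bias would run the other way if history were more common in the rivaroxaban group.

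**The case against.** The strongest reply is that the text does not compel the worst reading. Six months of enrollment is a minimum, so a reader who infers that eligibility or CHADS2 is capped at 6 months goes beyond the document; the CHADS2 look-back lies in a cited source. Operationalization is also partly deferred (Section 2.b). This stands for eligibility. It does not stand for adjustment, where Section 2.a states a flat 6 months and the deferral does not name the window.

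Stronger readings are tempting and should not be made:

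- *That the 1-year atrial fibrillation criterion cannot be applied.* Table 1 asks for evidence of "fibrillation within 1 year before and at least one day before the qualifying" ECG, but also requires that ECG within 30 days before randomization. Anyone meeting the trial's rule has atrial fibrillation documented well inside 6 months, and a claim in that window also lies within 1 year. Only the second, earlier piece of evidence could fall outside, and the plan does not say it will require one.
- *That valve exclusions are history criteria.* The entry "prosthetic heart valve (annuloplasty with or without prosthetic ring" and what follows describes a current state. An old valve could be missed if never recoded, but that is not a contradiction in the text.
- *That the new-user washout is 6 months.* The design is named without a washout length.
- *That 12 months of enrollment is needed.* That is a trade-off against sample size, not a correction.

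It is also fair that unmeasured confounding is named as the main limitation in Section 2.c, that more than 200 covariates are expected and some may act as proxies for stroke history, and that chronic conditions are often recoded within 6 months. These may reduce the bias. They do not explain why data already held should go unused.

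**Conclusion.** The point holds for the ROCKET emulation and for the history of stroke, TIA or systemic embolism. The stated covariate window is shorter than the criterion it has to serve, and nothing in the protocol reconciles the two. Older events that are not recoded would be entered as absent in the adjustment models, and possibly in eligibility and the 10% cap as well.

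Misclassification is a risk of unknown size, not a demonstrated fact. The 2% to 4% figure rests on assumed prevalences, an assumed doubling of risk, assumed capture rates and a single confounder taken in isolation. No effect on the agreement criteria in Section 9.a has been shown. The LEAD-2 medication look-backs in Table 2 are 3 months, so the 6-month window covers them. The change is worth making because it is specific and cheap and uses data the project will already hold.

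**What to change.** - Keep the 6-month minimum enrollment, and keep the 6-month window for laboratory values and recent medication use.
- For ROCKET, ascertain prior stroke, TIA and systemic embolism, and the other chronic CHADS2 components (heart failure, hypertension, diabetes), over all available pre-baseline claims. Section 1.d lists data from 1994 but expects to restrict the ROCKET analysis to 2011 onwards, so state expressly that claims before 2011 may supply history.
- State that eligibility, CHADS2, the 10% cap and the adjustment models use the same look-back for these variables.
- Repeat the analysis with the fixed 6-month window as a stability analysis. A restriction to patients with 12 months of prior enrollment could be a further one, but need not be a requirement.

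The cost is a few sentences of protocol text, some code and one more stability analysis. The drawback is that look-back length will vary between patients and may differ between treatment groups, so history would be found more readily in those enrolled longer. Report the distribution of look-back length by treatment group; the 6-month repeat, which gives everyone the same window, shows whether it matters.
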